### **8.2.2. Exclusion criteria**

Patients meeting any of the following criteria will not be included in the study:

- 1) Enrollment in an interventional clinical trial during the study observation period since clinical trial participants may have clinical scenarios that deviate from the population of interest.
- 2) Evidence of prior treatment with CDK 4/6 inhibitors (ribociclib or abemaciclib) in the metastatic setting.
- 3) Receipt of treatment indicated for another primary cancer during the study observation period or history of another primary cancer within the USON iKM EHR database.

---

\* Diagnosis of hormone receptor-positive/human epidermal growth factor receptor 2-negative breast cancer (BC) will be determined through a review of iKM's discrete diagnosis fields, which are populated during the routine course of care (International Classification of Diseases [ICD] codes will not be used). To identify patients with metastatic disease status, patients must have at least one of the following indicators: 1) receipt of a numbered LOT, 2) Stage IV disease, 3) Tumor, Node, Metastasis (TNM) staging with M value of 1, 4) record of location of metastatic disease or 5) current or prior disease status containing reference to metastatic disease.

† Visits are defined as physical encounters with the practice, detected by vital sign records. The second and third visits must be observed after the index date to demonstrate continuity of care. There is no required time span between the additional visits and the index date.

4) Initiated first treatment more than 120 days after metastatic date.

### 8.2.3. Cohort definitions and stratifications

Patients who meet the eligibility criteria described in **Sections 8.2.1-8.2.2** will be classified into the following cohorts described in **Section 8.1**.

As supported by the final sample size, each of the results tables and figures will be stratified to present the data for the following stratifications:

- Menopausal status (pre-, peri-, and post-menopausal) – post-menopausal only
- Metastases (visceral vs. non-visceral, bone only vs. non-bone only)
- Metastatic status (de novo versus relapsed/recurrent)
- Stage at diagnosis (I/II, III, IV or not documented)
- Number of metastatic sites (1, 2 and  $\geq 3$ )
- Prior adjuvant endocrine therapy (both prior to and after metastases)
- Prior adjuvant chemotherapy (both prior to and after metastases)
- Age stratifications (e.g., 18-50, 51-69,  $\geq 70$ ) also  $<65$  years and  $\geq 65$  years
- Race (White, Black, other, not documented)
- Palbociclib starting dose (75 mg, 100 mg, and 125 mg starting dose)
- Eastern Cooperative Oncology Group (ECOG) performance status score (0/1, and 2+) 90 days prior to index
- Disease-free interval from end of adjuvant treatment ( $< 12$  months,  $\geq 12$  months)

### 8.2.4. Chart review selection

For an initial feasibility assessment, all patients who meet the eligibility criteria described in **Sections 8.2.1-8.2.2** were included in the interim analysis. A subset of patients (n=1035) who initiated PB+FUL and **CCI** in the first- through third-line setting were selected for chart review.

During the course of abstraction, patients' eligibility for the study was verified and some of these patients were found to be ineligible. Reasons for disqualification are presented.

### 8.3. Variables

**Table 2** presents the list of variables that will be considered for this study. Most data will originate from 1 of 2 sources: the iKM EHR database (structured data) or chart review (unstructured data), although some variables may be derived from these raw data sources (e.g., age from date of birth). Derived and transformed data needed for the analysis are described and presented along with the operational definitions in the table below.

For variables that are listed as being sourced from both structured and unstructured fields, chart review is recommended and, in some cases, may be required. Specifically, many of these are variables that are available in structured fields but have been found to be more reliably and comprehensively captured through chart review of unstructured fields. Other variables require information that can only be sourced through chart review (e.g., response and progression). Data elements listed as being “not reported” will be used to determine eligibility or in calculations of derived variables.

Variables described as being captured at “baseline” will be captured at the date closest to the index date initiation within 30 days (90 days for performance status). Variables described as being captured with “prior medical history” will be sourced from patients’ entire medical history within the USON prior to index treatment initiation. Other variable assessment periods are indicated below. If multiple values are available during the time period of measurement, the one closest (in absolute value) to treatment initiation will be used.

Some data elements will be captured from both iKM and chart review. Since the chart review data are expected to provide a richer source of information, if data are available from both sources for a single patient, then chart review data will supersede what is available in the structured iKM data for the final analysis.

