## 8.2. Setting

The study population will consist of patients with a diagnosis of hormone receptor-positive/human epidermal growth factor receptor 2-negative mBC who initiated a who initiated PB+FUL and CCI

The USON includes 1,200 affiliated physicians operating in over 470 sites of care across states and treats approximately 1 million US cancer patients annually.

**Figure 1** presents a graphical depiction of the study time periods, which are as follows:

- Study observation period: 01 February 2016 – 30 June 2020.\*
- Study identification period: 01 February 2016 – 31 December 2019.
- Index date: The date of initiation with PB+FUL or CCI during the study identification period. For PB+FUL, the date of the first administration of either drug will be used.
- Baseline: Assessment will be done for the data collected at the closest date prior to index within 30 days of index (in absolute value). Variables to be assessed at baseline are specified in **Table 2**.
- Prior medical history: Patients' available history in the iKnowMed (iKM) EHR will vary based on the length of disease and the time within the USON. The prior medical history period will end the day prior to the index date. Variables to be assessed with prior medical history are specified in **Table 2**.
- Follow-up: Patients will be followed through the end of the study observation period, date of last visit or date of death, whichever occurs first. For analysis, patients will have a potential of at least 6 months of follow-up duration; however, patients will have variable follow-up time periods, depending on their index dates and last contact dates.

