## Palbociclib (IBRANCE)

## Study Number A5481128 NON-INTERVENTIONAL STUDY PROTOCOL

Protocol Version 2, August 30, 2021

	chart review			
Date of birth	iKM structured data	Eligibility; Data linkage; Baseline characteristic	Prior medical history	Patient's date of birth as recorded in iKM. This information will not be disclosed to the study sponsor.
Age	iKM structured data (derived)	Eligibility; Baseline characteristic	Baseline	Patient's age (in years) at the date of diagnosis, which will be calculated as the integer of [(diagnosis date – date of birth + 1) / 365.25]. Patients aged less than 18 years at the initial recorded diagnosis of mBC will be excluded from the study.
Age groups	iKM structured data (derived)	Baseline characteristic	Baseline	Multiple age categories will be created based on the continuous age data: Age (<18 years, 18-50 years, 51-70 years, $\geq$ 71 years) No information
Race	iKM structured data	Baseline characteristic	Prior medical history	Categorized as: White or Caucasian Black or African American Asian Native American Other No information The specific categories outside of White/Caucasian and Black/African American will be confirmed after reviewing sample sizes and the added value to the study with McKesson's Privacy and Compliance team.
Height	iKM structured data	Baseline characteristic	Baseline	Patient's height in meters.
Weight	iKM structured data	Baseline characteristic	Baseline	Patient's weight in kilograms.
Body mass index (BMI) at index date	iKM structured data (derived)	Baseline characteristic	Baseline	BMI = Weight (in kilograms)/(Height (in meters))  Based on the resulting BMI values, patients will then be categorized as underweight (BMI < 18.5), normal (BMI 18.5 – 24.9), overweight (BMI 25 – 29.9), obese (BMI $\geq$ 30) or no information (missing height or weight data).
Smoking history	iKM structured data	Baseline characteristic	Baseline	Categorized as: Never smoked Current smoker Former smoker No information
Family history of cancer	Chart review	Baseline characteristic	Prior medical history	Categorized as: Yes No
Menopausal status	iKM structured data + chart review	Baseline characteristic	Baseline	Categorized as documented by physicians: Pre-menopausal Peri-menopausal Post-menopausal No information

PFIZER CONFIDENTIAL

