Menopausal type	Chart review	Baseline characteristic	Prior medical history	If patients were menopausal, whether it was natural or induced and, if induced, the method (luteinizing hormone-releasing hormone [LHRH] suppression, surgical, other).
Healthcare setting and provider characteristics				
Practice location	iKM structured data (derived)	Baseline characteristic	Baseline	
The US census region of the USON clinic where the patient received care at the index visit:
 
Midwest: Illinois, Indiana, Michigan, Ohio, Wisconsin, Iowa, Kansas, Minnesota, Missouri, Nebraska, North Dakota and South Dakota
 
Northeast: Connecticut, Maine, Massachusetts, New Hampshire, Rhode Island, Vermont, Pennsylvania, New Jersey and New York
 
South: Delaware, Florida, Georgia, Maryland, North Carolina, South Carolina, Virginia, Washington D.C., West Virginia, Alabama, Kentucky, Mississippi, Tennessee, Arkansas, Louisiana, Oklahoma and Texas
 
West: Arizona, Colorado, Idaho, Montana, Nevada, New Mexico, Utah, Wyoming, California, Oregon and Washington State
 
Missing clinic values will be captured in a "no information" category.
 
Some of the regions may need to be collapsed if there are small sample sizes (e.g., South versus non-South). This determination will be confirmed after reviewing sample sizes and the added value to the study with McKesson's Privacy and Compliance team.

				CCI
Practice size	iKM structured data (derived)	Baseline characteristic	1/1/2018 – 12/31/2018	
The number of patients seen at the USON clinic where the patient receive care for his/her index visit in the year 2018:
 
<50 patients/ year 50-99 patients/year 100-149 patients/year ≥ 150 patients/year

Physician BC patient volume	iKM structured data (derived)	Baseline characteristic	1/1/2018 – 12/31/2018	
The number of BC patients seen by the physician who provided care for the patient's index visit in the year 2018:
 
<10 patients/ year 11-49 patients/year ≥ 50 patients/year

Physician specialty	iKM structured data	Baseline characteristic	Baseline	
Specialty of the physician who provided care for the patient's index visit:
 
Hematology & medical oncology Internal medicine Other

				Not documented

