Comorbidities	Chart review	Baseline characteristic	6 months prior to index	
Comorbidities documented within 6 months prior to or on the index date will be captured and summarized as:
 
Atrial fibrillation Bradyarrhythmia Cerebrovascular disease Congestive heart failure Chronic pulmonary disease Connective tissue disease Dementia Diabetes with end organ damage Diabetes without end organ damage Depression Electrolyte abnormalities Hemiplegia HIV/AIDS Hyperlipidemia Hypertension Infection Leukemia Long QT syndrome (congenital) Long QT syndrome (drug induced) Lymphoma Metastatic solid tumor (other than breast cancer) Mild liver disease Moderate to severe renal disease Myelosuppression Myocardial infarction Peptic ulcer disease
																					

				Peripheral vascular disease Tachycardia Stroke Unstable angina Venous thromboembolism (pulmonary embolism or deep vein thrombosis)
Disease histology	iKM structured data	Baseline characteristic	Baseline	Categorized as: Ductal Lobular Mixed Metaplastic Tubular Mucinous Other No information
Breast cancer gene (BRCA) 1/2 status	Chart review	Baseline characteristic	Medical history prior to index	Categorized as: Positive Negative No information
Estrogen receptor 1 gene (ESR1) status	Chart review	Baseline characteristic	Medical history prior to index	Categorized as: Positive Negative No information
Next generation sequencing (NGS) status	Chart review	Baseline characteristic	Medical history prior to index	Categorized as: Positive Negative No information
Treatment characteristics				
Prior adjuvant hormonal treatment	iKM structured data + chart review	Treatment characteristics	Medical history prior to index	The proportion of patients with prior adjuvant hormonal treatment for breast cancer prior to the index treatment.
Prior neo-adjuvant/adjuvant chemotherapy	iKM structured data + chart review	Treatment characteristics	Medical history prior to index	The proportion of patients with prior neo-adjuvant/adjuvant chemotherapy for breast cancer prior to the index treatment.
Prior metastatic hormonal treatment	iKM structured data + chart review	Treatment characteristics	Medical history prior to index	The proportion of patients with prior metastatic hormonal treatment for breast cancer prior to the index treatment.
Adjuvant treatment end dates	iKM structured data + chart review	Treatment characteristics	Medical history prior to index	Date of adjuvant treatment discontinuation.

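### Disease histology is held to the 30-day baseline window, so a type recorded only at an earlier diagnosis becomes 'No information'; menopausal status needs a rule for older entries.

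*Protocol*

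**What the plan says.** Protocol 8.3, repeated in SAP 5.4, states that baseline variables "will be captured at the date closest to the index date initiation within 30 days (90 days for performance status"; the bracket holds the only exception. Protocol 8.2 and SAP 2.1.1 word the period slightly differently: "Assessment will be done for the data collected at the closest date prior to index within 30 days of index (in absolute value".

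In Protocol Table 2 (SAP Table 1 is the same), the row "Disease histology" has iKM structured data as its only source and baseline as its period. Its values are "Categorized as: Ductal Lobular Mixed Metaplastic Tubular Mucinous Other No information".

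Menopausal status also has the baseline period, but is sourced from structured data plus chart review: "Categorized as documented by physicians: Pre-menopausal Peri-menopausal Post-menopausal No information". Menopausal type, in the next row, is read from the whole prior history: "If patients were menopausal, whether it was natural or induced and, if induced, the method".

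Exclusion criterion 4 removes patients who "Initiated first treatment more than 120 days after metastatic date". SAP section 6 reports missing values and does not impute them.

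**The concern.** A tumour's histological type is established at diagnosis and does not need to be re-entered when treatment for metastatic disease starts. The cohort includes relapsed patients (Protocol 8.2.3), whose initial diagnosis precedes the metastatic one. A 30-day window suits weight, which changes. For histology it can discard a valid value for no gain in accuracy.

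Baseline clinical characteristics are primary objective 1, so the reported histology mix is part of the main result. If the values lost belong mainly to patients with older diagnoses, the mix among patients with known histology would lean toward de novo disease.

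Menopausal status is used more widely. It defines a stratification (Protocol 8.2.3, SAP 4.4) and is among the example propensity-score covariates (Protocol 8.7.3, SAP 7.1). A status documented shortly before the window would be dropped from both uses.

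**Working it through.** The plan gives no missingness figure for either variable, so there is no number to reproduce. The check sets the definitions side by side.

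**1. Reach of the window.** Protocol 8.3 gives 30 days and no direction. Protocol 8.2 speaks both of a date before index and of absolute value. Whether the window is one-sided or two-sided, it reaches back no more than 30 days.

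**2. How comparable items are treated (Protocol Table 2).**

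| Variable | Source | Period |
|---|---|---|
| Disease histology | structured only | baseline (30 days) |
| Stage at diagnosis | structured only | all history before index |
| Hormone receptor status | structured + chart | all prior history |
| BRCA 1/2, ESR1 status | chart | all history before index |
| Date of initial diagnosis (uses iKM diagnosis and histology fields) | structured + chart | all history before index |

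Histology is the diagnosis-linked item in this list with the short window. The plan already searches the iKM histology field over the full history when it establishes the diagnosis.

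**3. Where an earlier record can lie.** In a first-line patient, the metastatic date may precede first treatment by up to 120 days: 120 − 30 = 90, so it may lie up to 90 days outside the window. In a relapsed patient the initial diagnosis is earlier still, and the documents set no limit on how much earlier.

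**4. What happens to such a record.** The rule in 8.3 for multiple values chooses only among values inside the period. There is no carry-forward rule, and the row's fallback is *No information*. SAP section 6 excludes imputation, although Protocol 8.7.2 leaves that to the sponsor. Chart review is not listed as a source, so it cannot restore the value.

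**5. Size.** Let f be the share of the 317 first-line patients (Protocol Table 3) whose only histology record lies outside the window. The number moved to *No information* is 317 × f. The documents do not give f. As a pure assumption, f = 10% gives 317 × 0.10 = 31.7, about 32 patients, and f = 75% gives 317 × 0.75 = 237.75, about 238. That range shows scale only; nothing in the documents places f within it.

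**6. Menopausal status.** The window attaches to the variable, not to the source. Chart review is a second source, but it does not by itself admit a status documented before the window. A patient could therefore have a menopausal type recorded from earlier history while her status is *No information*.

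**The case against.** The strongest case against the point concerns menopausal status. The documents do not say that it is recorded at diagnosis, only that it is as documented by physicians. It changes over time, chart data supersede structured data, and a value near index is a defensible target. All of that stands. What remains is narrower: there is no rule for a patient whose only status entry is older than 30 days.

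A reader might infer that the tables contradict themselves, because menopausal type has a full look-back and status does not. They do not. Type records how menopause came about, which is a historical fact; status is the state at index. Likewise, the initial-diagnosis row serves to establish the cancer and its date, not to report the histology category. These are differences of approach.

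A reader might also compare the 30-day window with the 120-day limit and take the ratio as a share of values lost. It is not one. The 120 days is a maximum gap from the metastatic date to first treatment, not a typical gap, and not the gap to the last entry of either variable. Nor would every patient without an entry in the window have an earlier one: Protocol Table 2 warns that records may be incomplete for diagnoses made outside the network.

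Finally, the documents do not say whether the histology field carries a biopsy date, an entry date or any date. If it is undated, or if programmers ignore the window for it, nothing is lost, and the text should then say so. Missing counts are to be reported, so any loss would be visible, though not its cause.

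**Conclusion.** The point holds for histology. As written, the plan applies to a fixed, diagnosis-linked attribute a window suited to changing values, unlike its treatment of stage, receptor status and BRCA/ESR1. The consequence rests on two assumptions: that the field is dated, and that the rule is applied literally. The number affected is unknown. The effect is on one descriptive row of the primary objective, because histology is neither a stratifier nor a named propensity-score covariate.

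Greater loss in relapsed patients is a plausible risk, because their diagnoses are older. A reader might go further and conclude that the histology mix will be biased toward de novo patients; the documents give no record dates or counts to show that.

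For menopausal status the defect is a missing rule for older entries, not a wrong target. It deserves attention because the variable feeds a stratification, itself conditional on sample size, and is an example propensity-score covariate.

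**What to change.** **Histology.** In Protocol Table 2 and SAP Table 1, set the period to all available history up to and including the index date, and use the most recent value. The existing prior-history label is not enough, because Protocol 8.2 ends that period on the day before index and would drop index-day entries.

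**Menopausal status.** Keep the near-index value when there is one. Otherwise use the last documented status on or before index from data already held, and report the age of that record. Do not carry forward automatically a status induced by LHRH suppression: the menopausal-type row lists this method, and the plan has no rule for suppression that later stopped.

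**Reporting.** For each variable, state how many values come from outside the 30-day window. This would settle the size of the problem.

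**Cost.** One changed cell and one added rule in each document, plus a re-query of the structured data. Chart review closed in December 2020. Protocol 8.4 says abstractors read the entire record, but nothing shows that older menopausal entries were stored, so the fallback should be limited to what is held. The downside is that some older menopausal entries may be out of date, which is why the age of the record should be shown.

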iKM use at practice location	iKM structured data	Eligibility criteria	Baseline	Patients who are treated at USON sites that utilize the full EHR capacities of iKM for their index visit will be eligible for participation in the study; otherwise, patients will be excluded.
Data accessibility	iKM structured data	Eligibility criteria	Baseline	Patients whose data are accessible for research purposes will be eligible for participation in the study; otherwise, patients will be excluded.
Disease characteristics				
Date of initial BC diagnosis	iKM structured data + chart review	Eligibility criteria, Baseline characteristic	Medical history prior to index	
To assess BC diagnoses that occurred prior to index, patients' available medical history in iKM will be searched. The completeness of this history will vary based on the length of disease and the time within the USON. Records may also be incomplete for patients with an initial BC diagnosis that occurred outside of the USON.
 
Diagnosis of BC will be determined through a review of iKM's discrete diagnosis and histology fields, which are populated during the routine course of care (International Classification of Diseases [ICD] codes will not be used).
 
If no initial diagnosis date is documented, the first recorded diagnosis date in iKM will be used. This date will be used in calculations, not reported separately.
 
Patients without a recorded diagnosis of BC will be excluded from the study.

Date of mBC disease diagnosis	iKM structured data + chart review	Eligibility criteria, Baseline characteristic	Medical history prior to index	
Date of first recorded diagnosis of metastatic disease within the EHR. Patients will be qualified initially based on the date identified in the structured data; this will be confirmed during chart review among patients selected for chart review. Ultimately, the primary source will be the chart if available.
 
Patients without recorded evidence of metastatic disease will be excluded from the study.
 
Structured data will confirm the patient as metastatic and as available, indicate the earliest associated date of any of these criteria:
 
 
1) Stage IV disease
 
2) Tumor, Node, Metastasis (TNM) stage with M value of 1
 
3) Record of location of metastatic disease
 
4) Current or prior disease status containing reference to metastatic disease
 

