Time since initial BC diagnosis	iKM structured data + chart review (derived)	Baseline characteristic	Medical history prior to index	The duration of time, in weeks, between the date of BC diagnosis and presentation of metastatic disease will be calculated for each patient and summarized as the mean ( $\pm$ SD) and median (range) of values. The number of patients with available data will be reported.

				Date of BC diagnosis and presentation of metastatic disease will be determined as defined above.
Time since mBC diagnosis	iKM structured data + chart review (derived)	Baseline characteristic	Medical history prior to index	The duration of time, in weeks, between the index date and presentation of metastatic disease will be calculated for each patient and summarized as the mean ( $\pm$ SD) and median (range) of values. The number of patients with available data will be reported. Presentation of metastatic disease will be determined as defined above.
Distant metastatic site(s)	iKM structured data + chart review	Baseline characteristic	Medical history prior to index	Baseline metastatic location(s) will be identified and categorized as: Bone (single) Bone (multiple) Brain Liver (single) Liver (multiple) Lung (single) Lung (bilateral) Lung (pleural effusion) Lymph nodes (regional) Lymph nodes (distant) Ovary Other No information Note, "no information" can indicate that metastases were not documented in the chart, not necessarily that patients did not have metastases.
Endocrine sensitivity at 12 months	iKM structured data	Baseline characteristic	Baseline	Patients who experienced relapse more than 12 months of completing adjuvant endocrine therapy will be considered to be endocrine sensitive; those who relapse in less than 12 months, endocrine resistant.
Endocrine sensitivity at 24 months	iKM structured data	Baseline characteristic	Baseline	Patients who experienced relapse more than 24 months of completing adjuvant endocrine therapy will be considered to be endocrine sensitive; those who relapse in less than 24 months, endocrine resistant.
Visceral/non-visceral status	iKM structured data + chart review (derived)	Baseline characteristic	Medical history prior to index	Categorized as: Visceral (asymptomatic or symptomatic*) Adrenal gland Bronchus Cervix Esophagus Gastrointestinal tract Genital organ Intestinal tract Kidney Large intestine Liver Lung Mediastinum Omentum Other respiratory organ Other urinary organ Ovary Pancreas

PFIZER CONFIDENTIAL

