				
Pericardium Peritoneum Pleura Rectum Retroperitoneum Small intestine Spleen
 
Non-visceral
 
Brain Breast Cervical nodes Chest wall Eye Ipsilateral supraclavicular lymph node Leptomeninges Other parts of nervous system Skin Spinal cord
 
Bone only
 
Bone Bone marrow Skull
 
Other
 
No information
 
The above list will be confirmed or updated after chart review is complete
 
*Asymptomatic visceral disease will be captured by chart review for patients who have explicit documentation of symptoms in the EHR records. All others will be assumed to be asymptomatic.

Count of metastatic site(s)	iKM structured data + chart review (derived)	Baseline characteristic	Medical history prior to index	
The total count of metastatic site(s) at index:
 
No documentation 1 2 3 4+
 
Note, “no documentation” can indicates that metastases were not documented in the chart, not necessarily that patients did not have metastases.

Stage at diagnosis	iKM structured data	Baseline characteristic	Medical history prior to index	
Categorized as:
 
Stage 0 Stage IA Stage IB Stage IIA Stage IIB Stage IIIA Stage IIIB Stage IIIC Stage IV No information

Eastern Cooperative Oncology Group	iKM structured data	Baseline characteristic	Up to 90 days prior to index	The ECOG performance status score is a rating of a patient's disease status, daily living activities and quality of life, with low

PFIZER CONFIDENTIAL

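### As written, the closest-to-index rule would let a Stage IV entry made at relapse stand as Stage at diagnosis, because that variable has no anchor to the initial diagnosis

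*Protocol*

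**What the plan says.** The general rule is in Protocol section 8.3 and is repeated word for word in SAP section 5.4: "If multiple values are available during the time period of measurement, the one closest (in absolute value) to treatment initiation will be used". It follows the descriptions of baseline variables, prior-history variables and other assessment periods. Its reference to the measurement period matches a column heading of the variable table. No variable is exempted.

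The row "Stage at diagnosis" (Protocol Table 2, SAP Table 1) gives structured iKM data as the only source and all medical history before index as the period. Its definition is a list of categories from Stage 0 to Stage IV plus a no-information level. It names no date to which the stage must belong.

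Other rows state their own selection rule where one is wanted. For the date of metastatic diagnosis, structured data are to "indicate the earliest associated date of any of these criteria", and Stage IV disease is the first criterion listed. The row for the initial breast cancer diagnosis date has its own fallback: the first diagnosis date recorded in iKM.

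Protocol section 8.2.3 and SAP section 4.4 stratify by "Stage at diagnosis (I/II, III, IV or not documented" and, separately, by "Metastatic status (de novo versus relapsed/recurrent". The second stratifier has no row in either variable table. Protocol section 8.7.3 and SAP section 7.1 name stage among the example propensity-score covariates.

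**The concern.** Weight and performance status are measured repeatedly, and the value nearest index is the right one to take. Stage at diagnosis is a fixed historical fact, and for a relapsed patient the record nearest index is the one least likely to describe the original diagnosis.

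Any error runs one way, into stage IV. It would also be hard to see: Stage IV is a plausible value for anyone in a metastatic cohort, so the checks for out-of-range and illogical values in Protocol section 8.8 need not flag it. Because the source is structured data only, the rule that chart review supersedes structured data offers no correction.

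What is at stake is the stage distribution reported under primary objective 1, the stage-stratified tables and curves, and covariate balance wherever stage enters the propensity model. De novo status would be affected as well if the analyst derives it from stage, which nothing in the plan prevents.

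**Working it through.** The plan gives no figure to reproduce. The check is a reading of the text, followed by an illustration of scale.

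**Step 1: which record the rule picks.** Take a patient diagnosed at stage II who relapses and then starts first-line treatment.
- The stage II entry dates from the original diagnosis, before the metastatic date.
- A Stage IV entry made at relapse and before index falls between the metastatic date and index.
- Both lie in the measurement period. The later one is always nearer index, so the rule picks Stage IV.
- Exclusion criterion 4 (Protocol section 8.2.2) removes patients who "Initiated first treatment more than 120 days after metastatic date". In a retained first-line patient such an entry is therefore normally within about 120 days of index, while the original stage may be years older.

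**Step 2: whether the row overrides the rule.** The metastatic-date row does so, by asking for the earliest date. The stage row has no equivalent. Only its name points elsewhere, and it does not say which diagnosis is meant, although the table keeps initial and metastatic diagnosis as separate rows.

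**Step 3: scale.** Inputs:
- N = 317, the final first-line PB+FUL count (Protocol Table 3).
- r = share of patients who are relapsed. **Assumed**; not in the documents.
- m = share of relapsed patients whose last stage entry before index is IV. **Assumed**; not in the documents.

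Simplification: every patient who is not relapsed is truly stage IV at diagnosis, and every patient has a recorded stage.

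Formulas:
- patients moved into stage IV = N × r × m
- true stage IV share = 1 − r
- recorded stage IV share = (1 − r) + r × m
- relapsed share of the recorded stage IV stratum = r × m / [(1 − r) + r × m]

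| r | m | Patients moved | Stage IV: true → recorded | Relapsed within stage IV stratum |
|---|---|---|---|---|
| any | 0 | 0 | no change | 0% |
| 0.40 | 0.10 | 317 × 0.04 ≈ 13 | 60% → 64% | 0.04/0.64 = 6.3% |
| 0.55 | 0.30 | 317 × 0.165 ≈ 52 | 45% → 61.5% | 0.165/0.615 = 26.8% |
| 0.70 | 0.50 | 317 × 0.35 ≈ 111 | 30% → 65% | 0.35/0.65 = 53.8% |

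The table shows how sensitive the result is to r and m. It does not estimate what will happen.

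**The case against.** The strongest reply is that the variable's name settles the matter: a Stage IV entry made at relapse is not a stage at diagnosis, so it is not one of the multiple values to which the rule applies. A careful programmer may well read it that way. Nor do the documents say that iKM adds or overwrites stage at relapse. M1 status, metastatic location and disease status can each flag relapse without a new stage entry. This stands as far as frequency goes: the effect may be zero. It does not remove the defect, because the written rule has no exemption and the row supplies no anchor.

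De novo status need not come from stage. The plan also collects the interval from initial diagnosis to metastatic presentation, adjuvant treatment and disease-free interval. That stands too, so contamination of the de novo stratum is possible but not established.

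Two stronger readings are tempting and fail.
- A reader might infer that the same rule discards earlier metastatic sites and shifts the site-count strata downward. The rows call for several sites: "Baseline metastatic location(s) will be identified and categorized as" a list that includes multiple-lesion levels, and "The total count of metastatic site(s) at index" has levels up to 4+. A single-site rule could not produce those totals. Chart review is also a source for both variables.
- A reader might infer that comorbidities are cut to the latest record. Their row already captures those documented in the six months up to and including index.

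**Conclusion.** The point holds for one variable. Followed as written, the rule gives the wrong value of Stage at diagnosis for any relapsed patient with a Stage IV entry made between relapse and index. This is a stated rule that conflicts with the meaning of the variable, and so more than a missing detail.

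The documents do not support saying that relapsed patients are, or will be, counted as stage IV at diagnosis. They give neither the relapsed share nor the frequency of re-entered stage, and the size ranges from none to large accordingly. Nor would every stratified result be affected: strata such as age, race, ECOG and starting dose do not use stage, and all stratification depends on sample size. The change is worth making because stage serves three purposes in the plan and the correction is cheap.

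**What to change.** In Protocol section 8.3 with Table 2, and in SAP section 5.4 with Table 1:

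1. Limit the closest-to-index rule to repeated single-value measures such as weight and ECOG.
2. Define Stage at diagnosis as the stage recorded at or nearest the initial breast cancer diagnosis date. Set it to the existing no-information level when only a later stage exists, or when the initial date is merely the first iKM record. The second condition matters because the plan warns that records may be incomplete for patients first diagnosed outside the network. Without it, a relapsed patient whose first iKM record is already metastatic would be labelled stage IV at diagnosis.
3. Add a row for de novo versus relapsed status, derived from that stage together with the interval from initial to metastatic diagnosis and any adjuvant treatment history.

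The cost is a few sentences in each document and a changed derivation. All inputs are already collected. More patients may fall into the no-information level, and their number should be reported. The footnote to Protocol section 8.7 says that a modified SAP leads to a protocol update and resubmission to the IRB, so the edits should go in together.
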